16.2.3.4. Analysis of Change in 8-point SMBG profile from baseline

8-point SMBG profile at a visit will be calculated using available pre-visit measurements in the diary (performed in the week preceding the visit).

Descriptive statistics will be presented for the actual and change from baseline to scheduled visits for SMBG profile.

Treatment group comparison will be done using the same MMRM model as the primary efficacy analysis (without imputing missing values). Estimates of the means, LSMeans (2-sided 95% CIs) as well as treatment difference at each visit will be presented.

For graphical display at scheduled visits the mean and SD plot will be prepared for the actual Overall SMBG average measurement by visit, LSMeans and 95% CI from the same MMRM model will similarly be displayed graphically.

16.2.4. SUBGROUP ANALYSIS

The effect of subgroups mentioned in [section 8.6](#) on the change from baseline HbA1c at week 18 will be examined by employing a MMRM model. The subgroups will be included in the model along with the treatment group. Additionally separate subgroup analysis within each subgroup mentioned in [section 8.6](#) will be performed same MMRM model for treatment comparison within each subgroups.

The similar subgroups will also be examined for the immunogenicity parameters for the percent binding and the incidence analysis of cross reactive antibody. Besides examine subgroup by treatment interaction for percent binding. Separate analysis for both percent binding and incidence will be performed for treatment comparison within each subgroup.

16.3. EXPLORATORY PK ANALYSIS

Exploratory PK analysis will be performed by Mylan PK/DM department.

Descriptive statistics of PK concentration values will be presented for each scheduled visits by treatment group.

Treatment group comparison will be done using the GLM model on log-transformed PK concentration values including treatment, visit, treatment-by-visit interaction, time of administration of glargine [morning and evening], all as fixed effects. If treatment-by-visit interaction is not significant, this term will be dropped from the model, the reduced model will be performed to produce the final analysis. If treatment-by-visit interaction is significant, then this interaction term and visit term will be drop from the model and final model will be performed by visit with only treatment and time of administration in the model.

Document: \sasdata\Mylan\Insulin_glargine\SYA22825\Biostatistics\Documentation\Protocol\MYL-1501D3003_SAP_V1_MAY2018

Author: [name]

Version Number:

1.0

Version Date:

04MAY2018

Template No: CS_TP_BS016 Revision 4
Effective Date: 01Apr2016

Reference: CS_WI_BS005

Analysis Plan Template

LSMeans for each treatment group and Geometric Mean Ratio between the treatment groups will be calculated. 2-sided 90% confidence intervals for the log transformed treatment difference and p-values will be provided.

17. QUALITY OF LIFE ANALYSIS

Not applicable.

18. SAFETY OUTCOMES

All outputs for safety outcomes will be based on the Safety Analysis Set. Percentages will be computed on the total number of subjects in each treatment group.

18.1. ADVERSE EVENTS

Adverse Events (AEs) will be coded using MedDRA central coding dictionary, Version 20.1.

An AE is defined as any untoward medical occurrence in a patient or clinical investigation patient administered a pharmaceutical product that does not necessarily have a causal relationship with the product. An AE can therefore be any unfavorable and unintended sign (including a new, clinically important abnormal laboratory finding), symptom, or disease, temporally associated with drug administration, whether or not related to the product.

The above definition covers also cases of:

Exacerbation of pre-existing diseases or conditions.

Pre-existing diseases or conditions (reported at time of screening in medical history) will not be considered AEs unless there is an increase in the frequency or severity, or a change in the quality of the disease or condition.

Events occurring in patients treated with the active comparator are also considered AEs.

An AE will be defined as treatment emergent (TEAE) if the first onset (or worsening in the case of pre-existing disease) is after randomization through follow-up visit or 14 days after last dose [for patients that do not have a follow-up visit].

See [Appendix 1](#) for handling of partial dates for AEs. In the case where it is not possible to define an AE as treatment emergent or not, the AE will be classified by the worst case; i.e. treatment emergent.

An overall summary of number of patients within each of the categories described in the sub-sections [below](#), will be provided as specified in the templates.

Treatment group comparison will be performed using Fisher's exact test. P-value for the corresponding two-sided test will be presented.

Listings will include TEAEs and Non-TEAEs.

Document: \sasdata\Mylan\Insulin_glargine\SYA22825\Biostatistics\Documentation\Protocol\MYL-1501D3003_SAP_V1_MAY2018

Author: [name]

Version Number:

1.0

Version Date:

04MAY2018

Template No: CS_TP_BS016 Revision 4
Effective Date: 01Apr2016

Reference: CS_WI_BS005

Analysis Plan Template

18.1.1. ALL TEAEs

Incidence of TEAEs will be presented by System Organ Class (SOC) and Preferred Term (PT) and also broken down further by maximum severity and relationship to study medication. The number of events will also be presented.

18.1.1.1. Severity

Severity is classed as mild/ moderate/ severe/ life-threatening/ death (increasing severity). TEAEs starting on or after the first dose of study medication with a missing severity will be classified as severe. If a patient reports a TEAE more than once within that SOC/ PT, the AE with the worst case severity will be used in the corresponding severity summaries.

18.1.1.2. Adverse Drug Reaction (Relationship to Study Medication)

All noxious and unintended responses to an investigational product related to any dose of the investigation products should be considered adverse drug reactions (ADRs). The phrase “responses to an investigational product” means that a causal relationship between an investigational product and an AE is at least a reasonable possibility. All AEs judged by either the reporting investigator or the sponsor as having a reasonable causal relationship to an investigational product will be designated as ADRs.

All AEs, with the causal relationship to the trial drug reported as “possible”, “probable” or “definite” will be considered ADRs. If the relationship to the trial drug is not given, then the AE must be treated as if the relationship were “possible”.

If a patient reports the same AE more than once within that SOC/PT, the AE with the worst case relationship to study medication will be used in the corresponding relationship summaries.

Frequency and percentage of patients having adverse drug reaction will be presented by treatment, SOC and PT.

18.1.2. TEAEs LEADING TO DISCONTINUATION OF STUDY MEDICATION

TEAEs leading to permanent discontinuation of study medication will be identified by using the Treatment withdrawn field in the CRF under “Action taken with study medication”.

For TEAEs leading to discontinuation of study medication, summaries of incidence rates (frequencies and percentages) by SOC and PT will be prepared.

18.1.3. SERIOUS ADVERSE EVENTS

Serious adverse events (SAEs) are those events recorded as “Serious” on the Adverse Events page of the (e)CRF. A summary of serious TEAEs by SOC and PT will be prepared.

Document:	\\sasdata\Mylan\Insulin_glargine\SYA22825\Biostatistics\Documentation\Protocol\MYL-1501D3003_SAP_V1_MAY2018		
Author:	[name]	Version Number:	1.0
		Version Date:	04MAY2018
Template No:	CS_TP_BS016 Revision 4	Reference:	CS_WI_BS005
Effective Date:	01Apr2016		

Analysis Plan Template

18.1.4. ADVERSE EVENTS LEADING TO DEATH

TEAEs leading to Death are those events which are recorded as “Fatal” on the Adverse Events page of the (e)CRF. A summary of TEAEs leading to death by SOC and PT will be prepared.

18.1.5. LOCAL OR SYSTEMIC ALLERGIC REACTION

The local and systemic allergic reactions are recorded on the adverse events page of the eCRF.

TEAE incidence of both local and systemic allergic reaction will be summarized by SOC and treatment group. A separate listing will also be produced which include only events of local or systemic allergic reaction.

18.1.6. DEVICE-RELATED ASSESSMENT

The relationship to the insulin glargine pen/needle and to the Humalog pen/needle are recorded on the adverse events page of the eCRF.

TEAE incidence will be summarized by SOC and treatment group for the insulin glargine pen/needle relationship and for the humalog pen/needle relationship and for both.

The incidence of device problems (even if not leading to an AE) will be summarized for each treatment group.

18.1.7. NON TEAEs

The non-TEAEs, the events occurred during the run-in phase before randomization, will be summarized separately. The frequency and percentage of patients experiencing non-TEAEs, serious non-TEAE, withdrawing during the run-in phase due to non-TEAE during run-in phase, Deaths before the active treatment start will be summarized. All enrolled patients who enter into the run-in period will be considered for this summary.

18.2. LABORATORY EVALUATIONS

Results from the central laboratory will be included in the reporting of this study for Hematology, Blood Chemistry and Urinalysis. A list of laboratory assessments to be included in the outputs is included in the [protocol section 6.5.2.3](#).

Presentations will use SI Units as provided by the central laboratory Q2.

Quantitative laboratory measurements reported as “< X”, i.e. below the lower limit of quantification (BLQ), or “> X”, i.e. above the upper limit of quantification (ULQ), will be converted to X for the purpose of quantitative summaries, but will be presented as recorded, i.e. as “< X” or “> X” in the listings.

The following summaries will be provided for laboratory data:

Document:	\\sasdata\Mylan\Insulin_glargine\SYA22825\Biostatistics\Documentation\Protocol\MYL-1501D3003_SAP_V1_MAY2018		
Author:	[name]	Version Number:	1.0
		Version Date:	04MAY2018
Template No:	CS_TP_BS016 Revision 4	Reference:	CS_WI_BS005
Effective Date:	01Apr2016		

Analysis Plan Template

- Actual and change from baseline by visit (for quantitative measurements). Descriptive summaries will be presented for the actual and the changes from baseline at each visit. Changes from baseline will be analyzed using the same MMRM model then the primary efficacy variable, but without any imputation. LSMeans for each treatment group and associated SE/2-sided 95% CI will be presented. Differences in LSMeans will also be calculated with the SE, 2-sided 95% CI and p-value.
- Incidence of markedly abnormal laboratory criteria. The number of patients and percentages will be provided for each treatment group at each visit for each markedly abnormal criteria.
- Shift from baseline according to normal range criteria (for quantitative measurements and categorical measurements)

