 - b. Clinical nephrotic syndrome or diabetic nephropathy with a serum creatinine level >1.5 times of upper limit of reference range at screening
 - c. History of severe form of neuropathy or cardiac autonomic neuropathy, recorded while collecting subject history. Subjects with mild or moderate forms of neuropathy will be allowed.
 - d. Subjects with a history of limb amputation as a complication of diabetes (at any time), or any vascular procedure during the 1 year prior to screening.
 - e. History of diabetic foot or diabetic ulcers in the 1 year prior to screening.
13. Any elective surgery requiring hospitalization planned during the study period.
14. Clinically significant major organ disorder at the time of screening including:
 - a. Uncontrolled hypertension, defined as stage 2 hypertension by Joint National Committee VII (even if therapy is ongoing, blood pressure \geq 160 mm Hg systolic or \geq 100 mm Hg diastolic).
 - b. Uncontrolled hyperlipidemia (even if therapy is ongoing, LDL >160 mg/dL or triglycerides >500 mg/dL).
 - c. Uncontrolled hyperthyroidism or hypothyroidism (subjects can be included if these conditions are controlled with thyroid hormones or anti-thyroid drugs).
 - d. Impaired hepatic function (alanine transaminase [ALT] or aspartate transaminase [AST] value >2 times the upper limit of the reference range and/or serum bilirubin 1.5 times the upper limit of the reference range at the screening visit). Subjects with evidence of Gilbert's disease may be included in the study if they have total bilirubin of <3 mg/dL with indirect bilirubin contributing to >80% of the total bilirubin.
15. History of a significant medical condition, such as:

- a. Clinically significant cardiac disease like unstable angina, myocardial infarction, grade 3 or 4 congestive heart failure (CHF) according to New York Heart Association criteria, valvular heart disease, cardiac arrhythmia requiring treatment, and pulmonary hypertension; during the year prior to screening.
 - b. Stroke or transient ischemic attack (TIA) in the 6 months before screening.

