7.3. RETESTS, UNSCHEDULED VISITS AND EARLY TERMINATION DATA

In general, for by-visit summaries, data recorded at the nominal visit will be presented. Unscheduled measurements will not be included in by-visit summaries, but will contribute to the scheduled visit if scheduled visit value is missing or the Last Observation Carried Forward (LOCF) value in case primary sensitivity analysis, or best/ worst case value where required (e.g. shift table) in safety analysis.

In the case of a retest (same visit number assigned), the earliest available measurement for that visit will be used for by-visit summaries.

Early termination data will be entered under the Visit 14 (week 18), but for summary tables it will be

Document:	\\sasdata\Mylan\Insulin_glargine\SYA22825\Biostatistics\Documentation\SAP\MYL-1501D-3004_SAP_Final_2_0_clean.doc		
Author:	[name]	Version Number:	2.0
		Version Date:	18OCT2018
Template No:	CS_TP_BS016 Revision 4	Reference:	CS_WI_BS005
Effective Date:	01Apr2016		

Analysis Plan Template

mapped to the next available planned visit number after their last scheduled visit. For example, should a patient discontinue at Visit 9, the Early Termination visit will have their Fasting plasma glucose and their HbA1c assay taken. The fasting plasma glucose would then be summarized under Visit 10 and the HbA1c under Visit 12.

Listings will include scheduled, unscheduled, retest and early discontinuation data.

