18.4. VITAL SIGNS

The following Vital Signs measurements will be reported for this study:

- Sitting Systolic Blood Pressure (mmHg)
- Sitting Diastolic Blood Pressure (mmHg)
- Pulse Rate (bpm)
- Respiratory Rate (breaths/min)
- Temperature (°C)

Document: \sasdata\Mylan\Insulin_glargine\SYA22825\Biostatistics\Documentation\SAP\MYL-1501D-3004_SAP_Final_2_0_clean.doc

Author: [name]

Version Number:

2.0

Version Date:

18OCT2018

Template No: CS_TP_BS016 Revision 4
Effective Date: 01Apr2016

Reference: CS_WI_BS005

Analysis Plan Template

- Weight (kg)

The following summaries will be provided for vital signs data:

- Actual and change from baseline by visit. Descriptive summaries will be presented for the actual and the changes from baseline at each visit. Changes from baseline will be analyzed using the same MMRM model than the primary efficacy variable, but without any imputation. LSMeans for each treatment group and associated SE/2-sided 95% CI will be derived. Differences in LSMeans will be calculated with the SE, 95% CI and p-value.
- Incidence of potentially clinically significant vital signs. The number of patients and percentages will be provided for each treatment group at each visit and overall visit (patient will be counted as clinically significant if at least one clinically significant occurred in all the visits. Fisher exact test will be performed between the treatment groups.
- Listing of patients meeting markedly abnormal criteria

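### SAP 18.2 reports the incidence of markedly abnormal laboratory values only visit by visit, so it can omit abnormalities that resolve before Week 18 and does not separate those already present at Week 0

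*SAP*

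**What the plan says.** The current text is SAP V2.0; V1.0 reads the same on the 18.2 and 7.3 rules used here.

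- **SAP 18.2, second bullet**, announces an incidence of markedly abnormal values and defines it visit by visit: "The number of patients and percentages will be provided for each treatment group at each visit for each markedly abnormal criteria." No overall or any-time count follows.
- **SAP 18.2.1** lists the criteria as fixed cut-offs (for example ALT above 3 times ULN, total bilirubin above 2 times ULN, glucose below 55 or above 270 mg/dL). None refers to the subject's baseline.
- **SAP 18.2, third bullet**, adds a shift table based on the normal range, which 18.2.1 divides into low, normal and high.
- **SAP 7.3** on unscheduled values: "Unscheduled measurements will not be included in by-visit summaries, but will contribute to the scheduled visit if scheduled visit value is missing." They may also serve as "best/ worst case value where required (e.g. shift table) in safety analysis." For retests, "the earliest available measurement for that visit will be used for by-visit summaries." Early termination results are mapped to the next planned visit. "Listings will include scheduled, unscheduled, retest and early discontinuation data."
- **SAP 18.4** treats vital signs differently: "The number of patients and percentages will be provided for each treatment group at each visit and overall visit." In 18.4.1 every vital-sign criterion includes a change from baseline.
- **Protocol V2.0, Table 1**, schedules hematology and blood chemistry at Visits 1, 6 and 14. Section 6.3.7 has early terminators complete the Visit 14 procedures.

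**The concern.** A table of incidence should show how many subjects in each arm developed a marked abnormality on treatment. With one scheduled on-treatment sample, a by-visit table for hematology and chemistry comes close to a Week 18 prevalence. It can fail in two ways. A transient abnormality detected between visits may be in the database but not in the table. An abnormality that predates randomized treatment is counted alongside new ones. The study sets out to show similar safety as well as efficacy. Of the three laboratory summaries in 18.2, this is the only one that uses limits more extreme than the normal range. Loss of real events, or dilution by pre-existing ones, makes the comparison less sensitive.

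**Working it through.** The plan states no figure for this table, so the check is mainly a reading of the rules, with one illustration.

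**1. Scheduled samples after Week 0 (Protocol Table 1)**

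| Test | Visits after Week 0 | Number |
|---|---|---|
| Hematology, chemistry | V14 | 1 |
| Lipids | V12, V14 | 2 |
| Fasting plasma glucose | V8, V10, V12, V14 | 4 |

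Fasting plasma glucose is analyzed separately as an efficacy variable. The glucose criterion in 18.2.1 stands under biochemistry.

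**2. What reaches the 18.2 table under SAP 7.3**

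| Chemistry result | In the by-visit table? |
|---|---|
| Scheduled Week 18 value | Yes |
| Early termination value | Yes, mapped to the next planned visit |
| Unscheduled value, Week 18 value missing | Yes, it fills in |
| Unscheduled value in Week 8, Week 18 value present | No, unless the worst-case clause is applied, which 18.2 does not invoke |
| Retest at the same visit | No, the earliest value is used |

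The fourth row is the gap. An ALT above 3 times ULN in Week 8 that has resolved by Week 18 appears in the listings but not in this table.

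**3. Whether the shift table closes the gap.** Suppose the worst-case clause brings that Week 8 value into the shift table. The value is then shown only as high. A subject slightly above ULN at baseline who rises above 3 times ULN moves from high to high. A normal-to-high shift does not distinguish a small rise from a marked one.

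**4. Baseline condition.** Entry limits apply at screening (Protocol 4.2.1 and 4.2.2), against the SAP 18.2.1 criteria:

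| Parameter | Entry limit | Marked criterion |
|---|---|---|
| ALT, AST | >2 × ULN excluded | >3 × ULN |
| LDL | >160 mg/dL excluded | >350 mg/dL |
| Triglycerides | >500 mg/dL excluded | >900 mg/dL |
| Hemoglobin | at least 9.0 g/dL required | <8.0 g/dL |
| Glucose | none stated | <55 or >270 mg/dL |
| Total bilirubin | Gilbert's subjects admitted below 3 mg/dL | >2 × ULN |

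For the first four, a Week 0 value beyond the marked limit is unlikely. Glucose has no entry limit. For bilirubin, subjects with Gilbert's disease "may be included in the study if they have total bilirubin of <3 mg/dL" (subject also to a condition on the indirect fraction). Such a subject can be beyond the marked limit at baseline only if 2 × ULN < 3 mg/dL, that is, ULN < 1.5 mg/dL. The documents give no ULN. If it were 1.0 to 1.3 mg/dL (assumption), the marked limit would be 2.0 to 2.6 mg/dL, below 3. At 1.5 mg/dL or more the example disappears.

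**5. How much one scheduled sample sees.** Assume onset is uniform over the 18 weeks and the abnormality lasts D weeks. Neither assumption comes from the documents. It is present at Week 18 only if it began in the last D weeks, so the probability is D/18:

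- D = 2: 2/18 = 11%
- D = 4: 4/18 = 22%
- D = 8: 8/18 = 44%

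This describes the sampling schedule. It does not measure how many recorded values the table leaves out.

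**The case against.** The strongest reply is that the SAP does not clearly exclude these values. The worst-case clause in 7.3 gives the shift table only as an example, so a programmer could apply it to the markedly abnormal table too. That is fair. The rule is ambiguous, and a reader who infers that the SAP bars all unscheduled laboratory values goes too far. They fill missing visits, early termination samples are mapped in, and everything is listed. But 18.2 does not call on the clause, so two programmers could produce different tables.

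A second reply is that important events have another route. Protocol 6.5.2.3 and 9.5 require clinically significant laboratory findings to be recorded as adverse events, and SAP 18.1 compares adverse events between arms with Fisher's exact test. Protocol 7.5.3 also plans a comparison of clinically significant abnormalities, which SAP 18.2 does not list. This lowers the stakes. It does not replace the table, because adverse event entry depends on the investigator's judgment, whereas the table applies a fixed threshold.

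Third, a reader might take the complement of D/18, 56% to 89%, as the share of events that the table loses and a change would restore. The documents do not support that. An abnormality for which no sample was drawn is in no dataset, and no table can recover it.

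Fourth, laboratory abnormalities are not among the secondary safety endpoints in Protocol 3.2.2, and 18.2 plans no test for this table. The same blinded rule applies to both arms. Randomization balances pre-existing abnormalities on average, so the expected harm is lower sensitivity. Nothing here shows a bias toward either process. All of this stands and limits the severity.

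**Conclusion.** The point holds as a minor weakness. Read as written, 18.2 with 7.3 gives by-visit counts only. When the Week 18 value exists, a marked hematology or chemistry abnormality seen only at an earlier unscheduled test is not counted. The criteria do not separate new abnormalities from those present at Week 0, which is an omission and not a stated rule. It matters mainly for glucose, and for bilirubin only under the ULN assumption above. The effect on the counts cannot be sized, because the number of unscheduled tests is not given. The SAP's own vital-sign section has both an overall count and baseline-referenced criteria, and no reason is given for treating laboratory values otherwise.

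**What to change.** In SAP 18.2, second bullet, add one overall row per criterion. It counts subjects with any post-baseline central-laboratory value meeting the criterion who did not meet it at baseline. State that it uses scheduled, unscheduled and early termination results, and retests unless the first result is shown to be a laboratory error, in which case the erroneous value is dropped. Keep the by-visit rows. This also settles whether unscheduled worst values belong in the table, and it follows the overall count in 18.4.

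The cost is a sentence or two in the SAP and one row per criterion in a planned table, using results already collected. There are two limits. Unscheduled tests are usually taken for cause, so the row shows worst values and not a random sample; a footnote should say so. Section 18.2 reports central-laboratory results, and the documents do not say where unscheduled tests are run, so any done locally would stay outside the table.
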